**February 2017 Amendment**

We amended the protocol to include subjects with a lower AUDIT score that would most likely NOT be referred by their Primary Care Provider (PCP) to the BHL for a Brief Intervention. However, as the National Institute on Alcohol abuse and Alcoholism (NIAAA) defines drinking while taking contraindicated medications as risky alcohol use: (<https://www.niaaa.nih.gov/alcohol-health/overview-alcohol-consumption/moderate-binge-drinking>), and thus a BI is still warranted. For subjects enrolled in the study with a low AUDIT score, the study counselors will perform the BI.

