e. **Summary of Findings from Our Research Program.** These studies demonstrate our ability to recruit large samples in a timely fashion, enroll Veterans who are engaging in risky drinking into research studies, deliver interventions over the telephone, and maintain high follow-up rates across periods as long as 24 months. Three of these studies also provide evidence to support the effectiveness of enhanced or extended interventions for patients who do not evidence a good initial response to alcohol/drug treatment.

I. **Purpose of the Project:** (Clearly provide the purpose of this research project.) In this application, we propose to test an integrated prevention intervention, designed to reduce rates of risky drinking in Veterans receiving prescription opioids for chronic pain management or opioid replacement therapy. For Veterans on opioid replacement therapy, they must have a chronic pain diagnosis. This adaptive, patient-centered intervention provides integrated clinical assessment, brief intervention, monitoring, and extended prevention services delivered through a combination of telephone calls, and text messages.

J. **Describe the Research Questions or Hypotheses** (that is, what questions are you trying to address by conducting the research.)

1. **Primary objective:** To compare the effectiveness of a 12-month prevention intervention (PI) with a brief intervention only group (BIO) over an 18-month follow-up period, for Veterans treated with prescription opioids and who are engaging in risky/hazardous drinking, based on NIAAA guidelines.
  - *Hypothesis 1:* PI will produce better outcomes than BIO, as indicated by lower rates of risky/hazardous alcohol use across the follow-up period.
2. **Secondary objectives:** To examine secondary outcome measures, moderator effects, and mediation effects:
  - *Hypothesis 1:* PI will produce better outcomes than BIO on frequency of heavy drinking, biological measures of heavy drinking (i.e., GGT and CDT), urine toxicology tests to assess other drug use, depression, and pain.
  - *Hypothesis 2:* Rates of opioid overdoses will be lower in PI than in BIO
  - *Hypothesis 3:* Intervention effects will be greater in higher-risk Veterans, including those with higher prescription opioid dosages, co-occurring benzodiazepine use, poor social support, and low readiness for change.

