  - *Hypothesis 4:* Results favoring PI over BIO on risky drinking will be mediated by greater readiness for change, self-efficacy, and coping.

K. **Primary Outcome Variable(s):** (Define the primary outcome variable(s) used to support the study objectives (e.g. if the objective is to show that treatment A is superior to treatment B in the treatment of subjects with essential hypertension, the primary outcome variable is blood pressure measurement.) **The primary outcome measure will be rates of risky drinking (i.e., more than 4 drinks at any one sitting or more than 14 drinks/week for men; more than 2 drinks at any one sitting or more than 7 drinks/week for women) (5) within each follow-up period, as determined by the TLFB.**

L. **Secondary Outcome Variable(s):** (Define the secondary outcome variables. Such measured variables should also include the timing of measurement.) **Secondary outcomes in the study will be self-reported frequency of heavy drinking days (TLFB), biological measures of alcohol use (%dCDT and GGT), urine toxicology tests to assess other drug use, VA records of opioid overdoses, depression, and pain.**

M. **Study Design and Methods:**

1. Is this a clinical trial?  YES  NO
  - 1.1. If yes, what type? Check all that apply.
 

Phase I  Phase II  Phase III  Phase IV
  - 1.2. If yes, this study must be registered on [Clinicaltrials.gov](https://Clinicaltrials.gov).

2. **Design**

- 2.1. What research methods will be used in the project? Check all that apply.

 Surveys/Questionnaires	 Interviews	 Audio Taping
 Behavioral Observations	 Chart Reviews	 Video Taping
 Focus Groups	 Randomization	 Double-Blind
 Control Group	 Placebo	 Withhold/Delay Treatment
 Specimen Collection	 Deception	 Telephone Survey
 Other (Describe)		

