According the NIAAA, any alcohol use with contraindicated medications (like opiates) is considered risky:

*Certain people should avoid alcohol completely, including those who:*

- *Plan to drive a vehicle or operate machinery*
- *Take medications that interact with alcohol*
- *Have a medical condition that alcohol can aggravate*
- *Are pregnant or trying to become pregnant*

[\(https://www.niaaa.nih.gov/alcohol-health/overview-alcohol-consumption/moderate-binge-drinking\)](https://www.niaaa.nih.gov/alcohol-health/overview-alcohol-consumption/moderate-binge-drinking)

Risky drinking will be ascertained during the AUDIT-C. Usually when administering the AUDIT-C, individuals will give vague answers (i.e. “every now and then”) that require follow up questions. For instance, if a Veteran affirms a period of time when they drank 6+ drinks in the past year, the interviewer could ask, “When was the last time that happened?” When asking about consumption the interviewer will be able to ascertain if the Veteran’s level of consumption meets this threshold (questions two and three) either with the Veteran’s initial response or with follow up questions.

We have also included language on how this will affect standard care through the BHL. As Veterans will be referred with lower levels of alcohol use (but still risky), after BHL triage it is possible that these Veterans will not receive a brief intervention.

Further, our business office is moving away from using petty cash to compensate research participants. Instead, we are switching to the Greenphire ClinCard system. ClinCard functions like a Visa debit card, and money can be loaded on to the card remotely by study staff. Our protocol has been updated to describe the system, how it functions, how Veterans will be paid.

**March 2018 Amendment**- We are changing the name of the study to something that sounds less threatening to Veterans who may fear losing their opiate prescription if they admit to drinking alcohol. We plan to change it to "Assisting Veterans in the Safe Use of Prescription Opioids."

Further, we plan to change the inclusion criteria to include Veterans on prescription opiates for chronic pain regardless of whether or not they admit to drinking alcohol.

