As part of broadening the inclusion criteria we plan to add a third group to the adaptive intervention. We will enroll and randomize the Veterans who do not admit to drinking and place them in a monitoring category where we continue to assess them and if they admit to consuming any amount of alcohol we would then transfer them to the treatment arm into which they had been randomized. This change is a significant change to the study but does not change the aims or outcomes and it does not increase the risk. It is a change supported by the DOD as a way to increase enrollment and reach veterans that we think may be less truthful about their alcohol use out of fear that they will have their opiate prescriptions taken away.

Following up those who initially deny drinking will provide important data for the VA. The yearly AUDIT screening appears to be underestimating the numbers of vets who are drinking alcohol. If our data indicate that a significant percentage of those who deny drinking at the start of the study end up reporting drinking later in the follow-up, it will be in indication that at risk patients (i.e., those on opioid meds) are at risk due to underreporting of their drinking, which could be an unintended consequence of the current VA policies.

We also will no longer be using the AUDIT-C.

Additionally, we have decreased the total n for the study to 150 from all sites. That is, 200 subjects from all sites being randomized (with 150 participants drinking and entering TX phase and 50 participants not drinking (25 at CMCVAMC and 25 at Penn).

Moreover, there is a personnel change. [name] is no longer a Research Coordinator on this study.

Lastly, SenseHealth has changed its name to Wellpass and the TRC has moved its location to [name]

At the time of this amendment, the following number of subjects have been randomized at the following sites:

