The primary outcome measure will be rates of risky drinking (i.e., more than 4 drinks at any one sitting or more than 14 drinks/week for men; more than 2 drinks at any one sitting or more than 7 drinks/week for women) within each follow-up period (e.g., months 1-3, 4-6, 7-9, 10-12, 13-18), as determine by the TLFB. Secondary outcomes in the study will be self-reported frequency of heavy drinking days (TLFB), biological measures of alcohol use (%dCDT and GGT), urine toxicology tests to assess other drug use, VA medical records of opioid overdoses, depression, and pain. Outcome data will be analyzed using mixed effect regressions for continuous and categorical data (i.e., SAS) and various packages to examine mediation effects (i.e., MPlus). The alpha level for the primary outcome will be set at 5%.

Data quality will be monitored by random inspection of the completed forms by the research coordinator and any problems detected will be discussed with the PI. The Research prevention counselors will receive standardized training on the interventions, which are all manualized. Adherence to the manuals will be monitored using audiotapes and individual supervision provided by the clinical coordinator. If drift is observed the counselors will be re-trained.

Blind interim analyses of the data will be conducted at two points when 50 and 75% of the sample has been accrued. If the results show statistically overwhelming significant differences between groups, the study will be stopped (or one of the conditions stopped).

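### Lighter drinkers were admitted because any alcohol with opioids counts as risky, but no planned drinking outcome credits them for cutting down or stopping; only prevented escalation above the volume limits can count.

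*Combined protocol and SAP*

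**What the plan says.** **Objective (section J.1).** The target population is Veterans on prescription opioids "who are engaging in risky/hazardous drinking, based on NIAAA guidelines".

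**Entry.** The January 2017 amendment (section O) lowered the AUDIT-C entry score from 4 (3 for women) to 2, citing NIAAA: "any alcohol use with contraindicated medications (like opiates) is considered risky". The February 2017 amendment (end of section H.4) gives the same reason, that NIAAA "defines drinking while taking contraindicated medications as risky alcohol use". The March 2018 amendment dropped the AUDIT-C and any drinking requirement, and planned 200 randomised, "with 150 participants drinking and entering TX phase" and 50 not drinking. The inclusion criteria in R.2.1.1 contain no drinking level. Under section O, a Veteran not drinking at entry starts the assigned arm on reporting a drink at the 3-, 6- or 9-month visit.

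**Outcome (sections K and W.1).** The primary outcome is "rates of risky drinking (i.e., more than 4 drinks at any one sitting or more than 14 drinks/week for men" and "more than 2 drinks at any one sitting or more than 7 drinks/week for women"), scored from the TLFB "within each follow-up period (e.g., months 1-3, 4-6, 7-9, 10-12, 13-18"). The March 2018 amendment states that aims and outcomes are unchanged.

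**Secondary outcomes (section L).** The alcohol measures are heavy drinking days, %dCDT and GGT. J.2 describes the two blood markers as measures of heavy drinking. Blood is scheduled only at baseline and 18 months, and Veterans enrolled after 4/1/2019 have no 18-month visit.

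**Handling of baseline drinking.** Randomisation blocks on whether use is admitted, not on its level (M.2.2). The primary model lists group, time and their interaction (W.4.2a). Baseline drinking level is not among the moderators (W.4.2c).

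**The concern.** The protocol uses two meanings of risky drinking. For admitting lighter drinkers it means any alcohol taken with opioids; for judging the intervention it means exceeding volume limits. A Veteran can be risky under the first and not under the second from the day of entry.

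For such a Veteran, the change that the 2017 rationale calls for, less alcohol or none, is not captured by any listed drinking outcome. If many treated Veterans are in this position, a null primary result would be hard to read. It could mean that PI does not work, or that it reduced drinking in a range that the outcome does not register. The planned effect size could also be optimistic for the widened population.

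**Working it through.** **1. What the outcome can and cannot register.** Take a man on daily opioids who has two drinks every evening: 2 × 7 = 14 a week, which is not more than 14, and never more than 4 at a sitting.

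| Course during follow-up | Primary outcome | Heavy drinking days |
|---|---|---|
| Continues unchanged | not risky | none |
| Halves his intake | not risky | none |
| Stops | not risky | none |
| Has five drinks once | risky in that window | at least one |

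The last column assumes that a heavy day is one above the per-sitting limit; section L does not define it. The first three courses are indistinguishable. The fourth is visible, so preventing it does count.

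**2. The plan's own sample size.** W.4.1 (March 2018) gives 136 to 162 in total for 35% versus 20%, and 72 to 84 for a 20-point difference. The repeated-binary formula multiplies the two-proportion size per arm by (1 + (m − 1)ρ)/m and divides by (1 − loss). I used m = 5, two-sided 5%, 80% power, ρ = 0.3 and 0.4, and 10% loss. The last two settings are inferred, because the amendment does not give them.

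- 35% versus 20%: 137.9 per arm for a single measurement. The multipliers are 0.44 and 0.52. Then 137.9 × 0.44/0.9 = 67.4 and 137.9 × 0.52/0.9 = 79.7 per arm, so 136 and 160 in total (stated: 136 and 162).
- 35% versus 15%: 72.4 per arm, giving 72 and 84 in total (stated: 72 and 84).

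The stated figures reproduce closely. The calculation applies one contrast to everyone and makes no separate allowance for below-limit drinkers.

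**3. Size of a possible dilution.** The documents do not give the share f of treated Veterans below the limits at entry. Assume that 35% versus 20% holds only for above-limit drinkers, and that below-limit drinkers exceed the limits at 5% in both arms:

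control = (1 − f) × 0.35 + f × 0.05; PI = (1 − f) × 0.20 + f × 0.05.

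| f | Control | PI | Difference | Power, 150 treated, ρ = 0.3 / 0.4 |
|---|---|---|---|---|
| 0 | 35% | 20% | 15 points | 84% / 78% |
| 20% | 29% | 17% | 12 points | 71% / 63% |
| 30% | 26% | 15.5% | 10.5 points | 62% / 55% |

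**4. With credit for prevented escalation.** Suppose instead that 10% of below-limit drinkers escalate under control and PI gives the same relative reduction (0.20/0.35). Power is then 76% / 69% at f = 20% and 71% / 64% at f = 30%. The loss is smaller but does not vanish.

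**5. The opposite reading.** Suppose 35% versus 20% already describes the mixed population, with below-limit drinkers at 5% in both arms. There is then no dilution, but the 15 points must come from above-limit drinkers alone: 15/0.8 = 18.75 points at f = 20%, and 15/0.7 = 21.4 points at f = 30%.

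**The case against.** **Prevented escalation counts.** PI is meant to detect and prevent a return to hazardous use (H.8a), and Veterans whose drinking rises to risky levels move to the more intensive track (section O, PI overview). A reader might infer that below-limit drinkers cannot show any benefit. The documents do not support that; the gap is confined to change below the limits.

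**The threshold is not purely high-volume.** One sitting over the limit in a window of three or six months is enough. A woman who has three drinks once is scored as risky. The share of Veterans who cannot move is therefore smaller than the weekly limits alone suggest. Nor are these Veterans scored as successes at baseline: the outcome is scored only in follow-up windows.

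**The widening had other grounds.** January 2017 also argued that a score of two can indicate regular or heavy use. March 2018 rested on enrolment and suspected under-reporting. The 51 Veterans randomised by then (42 + 3 + 6) had entered under an AUDIT-C threshold. The any-alcohol argument belongs to 2017 only.

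**The planned rates may already fit a mixed population.** W.4.1 states 35% and 20% for the two conditions, in the same amendment that removed the drinking requirement. The prior trial in H.9a found 56% still drinking riskily under usual care at 12 months. With f = 20% at 5%, an overall 35% implies (0.35 − 0.01)/0.8 = 42.5% among above-limit drinkers, which is not implausible beside 56%. This stands: the loss of power is conditional, not shown.

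**The primary outcome is a legitimate choice.** The stated goal is reduction to non-hazardous levels. An any-use outcome alone would score a man who goes from 30 to 5 drinks a week as a failure. This argues for adding a measure rather than replacing the primary one.

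**Conclusion.** The mismatch is in the documents. Lighter drinkers were admitted on an any-alcohol definition of risk, treatment requires only that the Veteran is drinking, and no planned drinking outcome registers less drinking or abstinence below the volume limits.

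The size is not known. The fall from 15 to 12 or 10.5 points rests on three assumptions: a below-limit share of 20% to 30%, a rate near 5% in both arms, and 35% versus 20% holding only above the limits. It illustrates what is possible and does not show that the trial is underpowered.

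A reader might also infer that the volume-based conclusion should be confined to Veterans above the limits at baseline. That would change the primary population to a subgroup not used in randomisation. At f = 20% to 30% it would leave 120 to 105 of the 150, fewer than the 136 to 162 that the plan asks for. Baseline adjustment with a supportive display by status is the better course.

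**What to change.** 1. Keep the primary outcome and its randomised population.
2. Add as a secondary outcome, from the TLFB already collected at every visit, any alcohol use and the number of drinking days in each follow-up window. Allow for window length, since months 13-18 cover six months and the other windows three.
3. Classify each participant as above or below the section K limits on the baseline TLFB, and state the look-back period. If Veterans who report no drinking are in the analysis, give them their own category.
4. Include that status as a covariate in the primary model (W.4.2a), and report the primary effect by status as a supportive analysis.
5. In J.1, state which definition of risky drinking the objective uses.
6. In W.4.1, state whether 35% versus 20% is meant for all treated Veterans or only for those above the limits at entry.

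**Cost.** No new data, visits or change to the intervention. The price is one extra secondary comparison and a little more analysis and wording. Power for the any-use outcome cannot be calculated, because the documents give no rate of any drinking.

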- 2.2. Describe how randomization or other treatment assignment will be made. **Veterans who meet criteria for participation will be randomly assigned to one of the two treatment conditions. Urn randomization will be used to balance the groups on three factors: gender, benzodiazepine or other drug use, and age. We will also be blocking on whether the person admits use or not when we do the randomization, so we get equal numbers of non-users in each condition. Urn randomization is a kind of biased-coin randomization where probability of being assigned to a group decreases if the group is overrepresented and increases if the group is underrepresented. As the sample size increases, the randomization shifts from perfect balance to complete randomization.**
- 2.3. For retrospective research studies, provide the "look-back" period. (e.g., December 1, 1999 through December 31, 2008.) **n/a**

3. **Study Duration**

- 3.1. Provide the estimated length of time to enroll all subjects and complete the study. **2.5 years of enrollment, but 5 years total for study start up, enrollment, completion, and analyses.**
- 3.2. Explain the expected duration of subject participation including any follow-up. **18 months for patients enrolled prior to 4/1/2019; 12 months for patients enrolled after 4/1/2019**
- 3.3. Specify the projected date of completion of the proposed study. **5 years from date of funding.**

4. **Drug Information** (If not applicable state, "Not Applicable.") **Not Applicable**

- 4.1. Specify if the drug or biological agent is:
  - 4.1.1. FDA approved
  - 4.1.2. Used for off-label purposes
  - 4.1.3. Not yet FDA approved.
- 4.2. Include the FDA Investigational New Drug (IND) number for all non-FDA approved and off-label drugs, biological agents or nutritional supplements. If not applicable state, "Not Applicable."
- 4.3. Provide all relevant information about the drug
- 4.4. Explain any wash-out periods, rescue medications permitted and any type of medications not permitted while enrolled in the study.
- 4.5. Describe blinding and un-blinding procedures.

- 4.6. Include the dosage, route of administration, previous use, and the safety and efficacy information on any drug used for research purposes.
- 4.7. Describe rationale for the dosage in this study.
- 4.8. Justify why the risks are reasonable in relation to anticipated benefits and/or knowledge.
- 4.9. Describe where drug preparation will be done.

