#### **October 2015 Amendment**

Because of the potential subjects were concerned about the “integrated” aspect of the study and how it might influence their clinical care, we submitted an amendment to remove the integration of the study and leaving research notes summarizing their status will no longer be the default. We have contacted the DoD about this change, and they are fine with it. The “integrated” nature was not an important piece. At a yearly progress meeting for DoD grant recipients, most of the other SUD related project have made it a point to NOT integrate their interventions with veterans’s medical care, as it sharply reduces recruitment rates.

We have randomized 7 subjects. We will notify them of the change, and re-consent them.

**January 2016 Amendment** - An amendment to the protocol has been made adding two sites to the study, with the CMCVAMC being the coordinating site. We are adding VA Pittsburgh as well as recruiting veterans not seen by the CMCVAMC at the University of Pennsylvania site. These sites are being opened up to address the poor recruitment numbers at the CMCVAMC site.

There is also a change to where the data is housed. Now instead of data being housed on a secure server in the VA, it is housed on a secure server at the University of Pennsylvania. An Off-Site Storage form is included. Additionally, the Penn/PVAMC MOU is included.

Paper based data will ultimately be kept at the CMCVAMC. However, electronic data will be combined and stored at Penn. The direct data entry can be done at Pittsburgh, CMCVAMC, and Penn, as long as there is internet access.

**July 2016 Amendment** – An amendment to the protocol has been made to change the server back to the secure server at the VA. The reason for this is an issue with software and being able to get through the VA firewall for data entry.

Paper based data will ultimately be kept at the CMCVAMC. Electronic data for Pittsburgh and CMCVAMC will also be stored at the CMCVAMC. Penn data will be stored at Penn as there is no way to access the VA server from outside the VA.

**January 2017 Amendment** - Previously Veterans had to score a four or greater (females 3 or greater) on the AUDC during the initial phone screen to be eligible to participate in the study. We have lowered this threshold to a score of two, as this score can still be indicative of regular/heavy alcohol use that would place Veterans prescribed chronic opiates at risk.

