#### R. Subject Recruitment (characteristics of the study population)

1. Provide the planned or targeted enrollment at:
  - 1.1. CMCVAMC - 115 (90 undergoing treatment and 25 just being followed and not undergoing one of the treatment groups)
  - 1.2. Other sites - 60 (10 at VA Pittsburgh; 50 at Penn)
  - 1.3. Not applicable; chart review or use of previously collected data -

2. **Screening and/or Eligibility Requirements - Inclusion/exclusion criteria are the same for screening before and after consent, however, some assessments used to determine final eligibility (such as the SCID and the MINI) are only administered once the Veteran comes to the lab (which occurs after a positive phone screen)**

2.1. Describe and provide justification for:

2.1.1. Inclusion criteria: **To be eligible for participation, Veterans must: (1) currently be receiving daily treatment with a prescription opioid for chronic pain, OR receive a daily prescription for opiate replacement therapy and have a chronic pain diagnosis; (2) be between the ages of 18 and 75; (3) have a cell phone capable of receiving text messages; (4) and be willing to be in a study where they might receive text messages.**

**If at some point during follow-up research visit, if a subject admits to drinking they will move on to the treatment arm that they were randomized to upon entry into the study.**

2.1.2. Exclusion criteria: **Veterans will not be eligible if they: (1) meet DSM-V criteria for a moderate to severe alcohol or drug disorder (with the exception of nicotine abuse/dependence); (2) have a current psychotic disorder severe enough to require inpatient treatment; or (3) are participating in alcohol use treatment at the VA or elsewhere (with exception of screening and brief intervention at the VA); (4) are currently on palliative care or are being treated with opioids for cancer-related pain.**

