- 4.2. Define plans for data and statistical analysis, including key elements of the statistical plan, stopping rules and endpoints.
  - a. Primary objective: The responses for the primary hypothesis comprise five repeated binary measurements per participant indicating risky alcohol use over the follow-up points. Our main analyses will use mixed effects logistic regression models to compare the two groups on the rates of risky alcohol use. We expect that linear and quadratic trends will account for the patterns of use across time. If residual analyses suggest significant lack of fit, we will examine more general time trends using spline specifications. The main explanatory variable will be a binary factor indicating intervention group, together with terms for time trends, and for group by time interactions, if appropriate. Based on analyses of similar data, we expect that a random intercept model, possibly with an autoregressive repeated measures structure, should provide a good fit to the covariance structure of the repeated measures, although we will examine more general specifications, if necessary. The estimated regression coefficients for the group variable, and possibly for group by time interactions, will address our primary hypothesis. We will test whether estimated coefficients are different from zero, and will report estimates and approximate 95% confidence intervals.

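### Site is in neither the randomisation factors nor the primary model, although about a third of planned Veterans come from two added sites: a cheap gain in precision, not an error

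*Combined protocol and SAP*

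**What the plan says.** On allocation, M.2.2 states "Urn randomization will be used to balance the groups on three factors: gender, benzodiazepine or other drug use, and age" and adds "We will also be blocking on whether the person admits use or not when we do the randomization". Site is not among these factors, and nothing there says that assignment runs separately by site.

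The January 2016 amendment in section O states "We are adding VA Pittsburgh as well as recruiting veterans not seen by the CMCVAMC at the University of Pennsylvania site". Section R.1 gives the targets: "CMCVAMC - 115 (90 undergoing treatment and 25 just being followed and not undergoing one of the treatment groups" and "Other sites - 60 (10 at VA Pittsburgh; 50 at Penn". These sum to 115 + 60 = 175, so 60/175 = 34% come from the added sites. The March 2018 amendment in section O instead plans 200 randomised, of whom 150 drink and 50 do not, with 25 of the non-drinkers at Penn.

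For the primary analysis, W.4.2.a states "The main explanatory variable will be a binary factor indicating intervention group, together with terms for time trends, and for group by time interactions". On the covariance it says "we expect that a random intercept model, possibly with an autoregressive repeated measures structure, should provide a good fit". No site effect, fixed or random, is named. W.4.2.b chooses the explanatory variables of the secondary models in the same way, so site is absent there too.

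**The concern.** When a trial grows from one centre to three, site is normally carried into the allocation, the analysis, or both. Penn is defined by a different source population. It also enrols mostly in a later period: at the March 2018 amendment, which admitted Veterans regardless of drinking, the Philadelphia VA had randomised 42 of its target of 115 (37%) and Penn 6 of 50 (12%). Site could therefore track the rate of risky drinking.

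If it does, any chance difference between arms in the share from Penn adds noise to the comparison of PI with BIO, and a model without site cannot remove it. At stake are some power in a trial whose sample size has already been cut, and how readily readers accept the result if the arms turn out visibly uneven by site.

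**Working it through.** **1. The plan's own sample size.** The March 2018 amendment in W.4.1 asks for 136 to 162 Veterans in total for 35% versus 20% at 80% power. The repeated-binary formula with five visits and two-sided 5% gives, per arm,

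m = [1.96·√(2·0.275·0.725) + 0.842·√(0.35·0.65 + 0.20·0.80)]² · (1 + 4ρ) / (5·0.15²)

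This is 60.7 at ρ = 0.3 and 71.7 at ρ = 0.4. With an assumed 10% loss these become 67.4 and 79.7, so 68 and 80 per arm, or 136 and 160 in total. The stated range is reproduced to within 2 Veterans. Site is not an input, so this point does not change the stated N.

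**2. Chance imbalance at Penn.** Take 50 Penn Veterans and near-equal arms. The number X of them in one arm of size n out of N is hypergeometric, with variance n·(50/N)·(1 − 50/N)·(N − n)/(N − 1). The standard deviation of the difference in Penn share is SD(X)·(1/n + 1/(N − n)).

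- N = 175 (all targets in R.1): SD(X) = 3.00; share difference 3.00·(1/87 + 1/88) = 6.8 points; P(30:20 or worse) = 13%.
- N = 150 (90 + 10 + 50): SD(X) = 2.90; share difference 2.90·(2/75) = 7.7 points; P(30:20 or worse) = 12%.

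Independent coin tosses would give 20%, but they let the arm sizes drift, which the urn limits.

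**3. The urn itself.** A simulated three-factor urn (3,000 runs; 90/10/50 Veterans; assumed factor prevalences of 10%, 30% and 50%) agrees. Without site, the share difference has a standard deviation of 7.6 points, and Penn splits 60:40 or worse in 13% of runs. With site as a fourth urn factor, these fall to 5.3 points and 3%. Because the totals conflict, other Penn targets were tried (25 and 75); the standard deviation without site stays at about 7 points.

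**4. Effect on the arm difference.** The shift equals the imbalance times the difference in risky drinking between Penn and the rest (the gap). At an assumed gap of 20 points, one standard deviation of imbalance moves the arm difference by 0.077·20 = 1.5 points. An imbalance of 15 points, near the 95% limit of the simulated urn, moves it by 0.15·20 = 3 points. For scale, the planned effect is 15 points. Its standard error at 75 per arm and ρ = 0.4 is √[(0.35·0.65 + 0.20·0.80)·(1 + 4·0.4)/(5·75)] = 5.2 points.

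**5. Error rate and power.** Beta-binomial data (ρ = 0.4, five visits, no dropout, N = 150 split 90/10/50, 20,000 runs) were analysed by a linear model on each Veteran's mean, with and without three-level site. This approximates the planned mixed logistic model. Type I error was 4.8 to 5.2% throughout, with or without site. Power for 35% versus 20%:

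| Assumed Penn gap | Without site | With site | Change |
|---|---|---|---|
| 0 points | 81.9% | 81.5% | −0.4 |
| 10 points | 81.2% | 81.4% | +0.2 |
| 20 points | 80.2% | 83.4% | +3.2 |
| 30 points | 78.2% | 85.3% | +7.0 |

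**The case against.** The strongest reply is that randomisation already covers this. Chance imbalance is counted in the standard error, the test keeps its size, and no site gap in drinking is documented. All of that stands. At gaps of 0 to 10 points the site term gains essentially nothing.

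A reader might also infer more than the documents support.

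- **Usual care differs by site.** For Pittsburgh, section O says that Philadelphia counselors deliver every brief intervention by phone with the same structure. For Penn, usual care is not described, so a difference is possible but not stated.
- **Overdoses are captured differently.** The source is VA records for everyone (L; W.1). Veterans not seen at the Philadelphia VA may use another VA. This is also a secondary outcome, which a site term in the primary model would not repair.
- **Penn's share of non-drinkers biases the result.** M.2.2 already blocks on admitted use, and the comparison of arms is overall. How many of Penn's 50 are non-drinkers is itself unclear, because 90 + 10 + 50 = 150 matches the planned number of drinkers.

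Finally, section G asks for content specific to the Philadelphia VA, and Y.1 mentions a separate Penn component. Assignment within site may therefore be described elsewhere. That limits the allocation half of the point. It does not limit the analysis half, because the power and analysis sections cover the pooled trial.

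**Conclusion.** Site is missing from both the stated allocation factors and the stated model, and Penn's source population differs by plan. The consequence is a modest loss of precision and of balance in the trial actually run. It is not bias on average and not an invalid test.

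The size depends on an undocumented quantity, the gap in risky drinking between Penn and the other sites. Over assumed gaps of 0 to 30 points, a site term changes power by between a loss of under 1 point and a gain of about 7. The figures also assume that Penn reaches 50; at the March 2018 amendment it had 6 of the 51 randomised, and a smaller Penn contingent would matter less. This is a worthwhile and inexpensive improvement, not an error in the plan.

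**What to change.** 1. In W.4.2.a, prespecify site as a fixed effect (Penn versus the Philadelphia and Pittsburgh VA sites combined), and state that it carries into the secondary models. Adjust the overdose comparison for site only if there are enough events. Pooling Pittsburgh avoids a sparse level of 10. This step works even if enrolment is complete.
2. In M.2.2, state whether assignment runs within site. If it does not, add site as an urn factor for the remaining assignments.
3. Fix the choice before outcomes are examined by arm. Section M.2.1 leaves the double-blind box unticked, so adding site after an imbalance is seen would be open to question.

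The cost is one model degree of freedom, up to about 1 point of power if site is not prognostic, and slightly looser balance on the other urn factors. Site is already known for every Veteran, so no new data are needed.
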